## **11.8 Modification of the Protocol**

Any changes that arise after the approval of the protocol must be documented as protocol amendments. Amendments (substantial/non-substantial) require regulatory approval and IRB/EC/REB approval or notification. Only after approval by CalciMedica, the PI, the IRB/EC/REB, and if applicable the regulatory authorities, will the protocol amendments become effective. In cases when the protocol is amended to enhance patient safety, the amendment may be implemented but must be immediately submitted to the IRB/EC/REB and regulatory authorities.

The revision number and date of the amendment will be recorded on the title page of the protocol.

The PI is responsible for informing the IRB/EC/REB of all problems involving risks to patients. In case of urgent safety measures, CalciMedica or its designee will immediately notify the PIs and relevant regulatory authorities.

## **11.9 Informed Consent**

Because the study will be conducted under a United States Investigational New Drug Application, informed consent that is in compliance with Title 21 of the United States Code of Federal Regulations (CFR) Part 50 will be obtained from each patient or LAR before the patient enters the study or before any unusual or non-routine procedure is performed. For sites outside the United States, the signed informed consent form will be obtained in compliance with local regulations, ICH E6 (1R) and the principles of the Declaration of Helsinki.

CalciMedica or its designee may provide to the PI or his/her study staff an informed consent form template. The informed consent form must be reviewed by CalciMedica or its designee before the PI or his/her study staff submits it to the IRB/EC/REB. After CalciMedica or its designee review the informed consent form, the PI or his/her study staff will submit it to the IRB/EC/REB for review and approval. If the informed consent form is revised during the course of the study, CalciMedica or its designee must agree with revisions before the PI or his/her study staff submits it to the IRB/EC/REB. The study staff must provide CalciMedica or its designee a copy of the revised informed consent form after IRB/EC/REB approves it. All patients or LARs affected by the revision must sign the revised informed consent form after the IRB/EC/REB approves it.

Before enrolling in the study, each prospective patient or LAR will receive a full explanation of the study and review the approved informed consent form. Once the PI or designee is assured that the patient or LAR understands the implications of participating in the study, he/she will ask the patient or LAR to give consent for the patient to participate in the study by signing the informed consent form.

A patient may participate in the study only after providing consent using an IRB/EC/REB approved informed consent form. A LAR of the patient may provide informed consent on behalf of the patient under conditions authorized by local laws and regulations. The patient or LAR must provide informed consent before the patient undergoes any study-specific procedures described in the protocol. The PI or designee will provide a copy of the informed consent form to the patient and/or LAR. The process of obtaining informed consent must also be documented in the patient source documents.

## **11.10 Protocol Violations and Deviations**

The PI or designee must document any protocol deviation or violation. Reporting of protocol deviations and violations to the appropriate IRB/EC/REB is the responsibility of the PI and must follow the applicable IRB/EC/REB guidelines.

If there is an immediate hazard to the patient, the PI may deviate from the protocol without prior approval from CalciMedica or its designee and the IRB/EC/REB but must notify CalciMedica or its designee and IRB/EC/REB of the deviation as soon as he/she is able to do so.

### **11.11 Financial Disclosure**

PIs and sub-investigators are required to provide financial disclosure information prior to starting the study. In addition, the PIs and sub-investigators must provide CalciMedica or its designee with updated information if any relevant changes occur during the course of the study and for one year following the completion of the study.

Any PIs, sub-Investigators or study staff with a vested financial interest in the success of the study may not participate in the study.

### **11.12 Sponsor Obligations**

CalciMedica or designee is not financially responsible for further testing/treatment of any medical condition that may be detected during Screening. In addition, CalciMedica is not financially responsible for the treatment of the patient's underlying disease.

### **11.13 Investigator Documentation**

Before beginning the study, the PI will be asked to comply with ICH E6 (R2) 8.2 and title 21 CFR by providing to CalciMedica or designee the following documents:

- An original signed investigator agreement page of the protocol
- The IRB/EC/REB approval of the protocol
- The IRB/EC/REB approved informed consent form
- Any written information regarding the study that will be provided to the patient or LAR
- A Form FDA 1572, fully executed, and all updates on new fully executed Form FDA 1572 (Unless granted an exemption by the FDA and in compliance with local regulations)
- Curricula Vitae for the PI and each sub-Investigator listed on Form FDA 1572. Evidence of licensure must be noted on the Curricula Vitae or a copy of the license must be provided. The Curricula Vitae must have been signed and dated by the PI and sub-Investigators within 2 years before study start-up to indicate that the documents are accurate and current
- Completed financial disclosure forms to allow CalciMedica or designee to submit complete and accurate certification or disclosure statements required under US Title 21 CFR 54. In addition, the PI and sub-Investigators must provide to CalciMedica or designee a commitment to update this information promptly if any relevant changes occur during the course of the study and for 1 year following completion of the study
- Laboratory certifications and normal ranges for any laboratories used by the site for the conduct of the study

## **11.14 Clinical Study Insurance**

CalciMedica has subscribed to an insurance policy, covering in its terms and provisions its legal liability for injuries caused to participating persons and arising out of this research that is performed strictly in accordance with the scientific protocol as well as with applicable law and professional standards.

## **11.15 Use of Information**

All information supplied by CalciMedica to the PI and his/her study staff is privileged and confidential. The PI and his/her study staff agree to use this information to accomplish the study and not to use it for other purposes without consent from CalciMedica. Furthermore, the PI and his/her study staff is obligated to provide CalciMedica with complete data obtained during the study. The information obtained from the clinical study will be used towards the development of CM4620-IE, and may be disclosed to regulatory authorities, other Investigators, corporate partners or consultants as required.

## **11.16 Publications**

CalciMedica Inc. reserves the right to review all planned communications and manuscripts based on the results of this study. This reservation of the right is not intended to restrict or hinder publication or any other dissemination of study results, but rather to allow CalciMedica to confirm the accuracy of the data, to protect proprietary information, and to provide comments based on information that may not yet be available to the study investigators. CalciMedica Inc. supports communication and publication of study results whatever the findings of the study. CalciMedica Inc. also encourages disclosure of any conflict of interest from all authors or investigators when manuscripts are submitted for publication.

## Appendix 1 Definition of Organ Failure

The definition of organ failure encompasses three organ systems, respiratory system, renal system and cardiovascular system.

For the respiratory system, organ failure will be defined as:

- PaO2/FiO2 ≤300, or
- SpO2/FiO2 ≤315, or
- The use of noninvasive or invasive mechanical ventilation

For the renal system, in patients without known chronic kidney disease, organ failure will be defined as:

- An increase in serum creatinine ≥300% if the baseline creatinine is known from prior to the hospitalization for acute pancreatitis, or
- A serum creatinine ≥1.9 mg/dL, or
- Urine output of <0.3 mL/kg/hour for ≥24 hours or anuria for ≥12 hours, or
- The initiation of renal replacement therapy

For patients with pre-existing chronic kidney disease (baseline GFR <60 mL/min/1.73 m^2), organ failure will be defined as:

- An increase in serum creatinine ≥300% if the baseline creatinine is known from prior to the hospitalization for acute pancreatitis, or
- An increase of serum creatinine to a level >4.0 mg/dl, or
- Urine output of <0.3 mL/kg/hour for ≥24 hours or anuria for ≥12 hours, or
- The initiation of renal replacement therapy

For the cardiovascular system, organ failure will be defined as:

- A systolic blood pressure <90 mmHg that is not fluid responsive, or
- The use of either vasopressor or inotropic support

The presence of organ failure will be assessed on Days 1-10.

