## 4 SELECTION OF PATIENTS

### 4.1 Inclusion Criteria

Patients must meet all of the following criteria to be randomized in a cohort:

1. Diagnosis of acute pancreatitis established by the presence of abdominal pain consistent with acute pancreatitis and 1 of the following 2 criteria:
  - a. Serum lipase or serum amylase > 3 times the upper limit of normal (ULN);
  - b. Characteristic findings of acute pancreatitis on abdominal imaging;
2. One of the following 2 criteria, either:
  - a. A SpO2 <96% with a FiO2 of 21% (room air) to 27% or a SpO2 <97% with a FiO2 ≥28%; Or
  - b. Diagnosis of SIRS, defined by the presence of at least 2 of the following 4 criteria:
    - i. Temperature < 36°C or > 38°C;
    - ii. Heart rate > 90 beats/minute;
    - iii. Respiratory rate >20 breaths/minute or arterial carbon dioxide tension (PaCO2) <32 mmHg;
    - iv. White blood cell count (WBC) >12,000 mm^3, or <4,000 mm^3, or > 10% immature (band) forms;
3. No evidence of pancreatic necrosis on contrast-enhanced computed tomography (CECT) performed in the 18 hours prior to consent or after consent and before Day 1;
4. Adults ≥ 18 years of age;
5. A female patient of child bearing potential who is sexually active with a male partner must be willing to practice acceptable methods of birth control for 365 days after the last dose of CM4620-IE;
6. A male patient who is sexually active with a female partner of childbearing potential must be willing to practice acceptable methods of birth control for 365 days after the last dose of CM4620-IE and must not donate sperm for 365 days;
7. Willing and able to, or have a LAR that is willing and able to, provide informed consent to participate, and to cooperate with all aspects of the protocol.

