### 8.11.7 Pulse Oximetry

A pulse oximetry measurement of oxygen saturation, (SpO2), will be measured at Screening and on Days 1 – 10. The PI or appropriately trained study coordinator will review the pulse oximetry waveform to attest to its adequacy. The FiO2 at the time of the pulse oximetry measurement will be recorded. For patients with assisted breathing, the FiO2 is read from the controlled oxygen source e.g. Venturi masks, ventilator and CPAP systems with calibrated oxygen blenders. For patients breathing unassisted i.e. room air, the FiO2 is recorded as 0.21. If a patient is on an uncontrolled oxygen source, the table below allows for the conversion of oxygen flow in L/min to FiO2:

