**Table 5 Conversion of O2 Flow to FiO2**

Supplemental Oxygen L/min	Estimated FiO2 (%)		
	Nasal Cannula	Face Mask	Face Mask with Reservoir
Room Air	21		
1	24		
2	28		
3	32		
4	36		
5	40	40	
6	44	50	60
7		50	70
8		60	80
9		60	90
10		60	95

Adapted from EPICII

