## **10.4 Statistical Analyses Plan**

A Statistical Analysis Plan (SAP) detailing the analyses for the study will be developed prior to the database lock. The SAP will serve as the final arbiter of all statistical analyses. Data will be summarized using descriptive statistics only. Continuous data will be summarized with number of patients (n), mean, median, minimum, maximum, standard of deviation, coefficient of variation and or geometric mean. Categorical data will be summarized with number and proportion of patients. The number of patients randomized in the study and the number of patients completing assessments for each Day will be summarized by cohort, sex and treatment arm. The number of patients and reasons for discontinuation of CM4620-IE or withdrawal from the study will be summarized.

Efficacy endpoints that will be analyzed will include, but not limited to, SIRS score, APACHE II score, CT severity index scores, classification indexes, organ failure scores, SOFA score, biomarker values and pain scores. These endpoints will be further detailed in the SAP.

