7.7 Secondary Endpoints – Organ failure

7.7.1 Definition

Respiratory Failure

The presence of respiratory failure will be assessed on Days 1-10.

Respiratory failure is defined as $\text{PaO}_2/\text{FiO}_2 \leq 300$, either determined by ABG or calculated from the $\text{SpO}_2/\text{FiO}_2$ or the use of non-invasive or invasive mechanical ventilation (respiratory support).

Renal Failure

- An increase in serum creatinine $\geq 300\%$ if the baseline creatinine is known from prior to the hospitalization for acute pancreatitis, or
- A serum creatinine ≥ 1.9 mg/dL, or
- The initiation of renal replacement therapy

For patients with pre-existing chronic kidney disease, organ failure will be defined as:

- An increase in serum creatinine $\geq 300\%$ if the baseline creatinine is known from prior to the hospitalization for acute pancreatitis, or
- An increase of serum creatinine to a level >4.0 mg/dl, or

- The initiation of renal replacement therapy

Cardiovascular Failure

The presence of cardiovascular failure will be assessed on Days 1-10. For the cardiovascular system, organ failure will be defined as:

- A systolic blood pressure <90 mmHg that is not fluid responsive, or
- The use of either vasopressor or inotropic support

Any Organ Failure

If the patient meets the conditions for at least one type of organ failure (respiratory failure, renal failure or cardiovascular failure), they have a diagnosis of Organ Failure. If they meet the conditions for more than one organ failure they also have a diagnosis of multiple organ failure. Patients free from all types of organ failure or without data to support diagnosis of organ failure, do not have organ failure

Transient organ failure

Patients with transient organ failure are identified by organ failure lasting less than 48 hours. Persistent organ failure is documented for greater or equal to 48 hours. New persistent Organ Failure is only applicable for patients without Organ Failure at baseline.

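### Under Protocol Appendix 1 with Table 5, a recorded FiO2 of 31.75% or more meets the SpO2/FiO2 criterion even at 100% saturation, so oxygen flow alone can trigger respiratory organ failure; SAP 7.7.1 leaves open whether this reaches the severity tables.

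*Protocol*

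**What the plan says.** **Protocol Appendix 1** gives three alternative routes to respiratory organ failure: PaO2/FiO2 of 300 or less, "SpO 2 /FiO 2 ≤315, or" noninvasive or invasive mechanical ventilation. Any one suffices. Organ failure is assessed on Days 1 to 10.

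**Protocol 8.11.7** says how FiO2 is obtained. On a controlled source it "is read from the controlled oxygen source e.g. Venturi masks, ventilator and CPAP systems with calibrated oxygen blenders". Otherwise: "If a patient is on an uncontrolled oxygen source, the table below allows for the conversion of oxygen flow in L/min to" FiO2. That table is Table 5, "Conversion of O2 Flow to FiO2".

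**SAP 7.7.1** has no 315 cut-off. It keeps ventilation and uses PaO2/FiO2 of 300 or less, "either determined by ABG or calculated from the" SpO2/FiO2. No formula is given. SAP Section 8, the place for changes from the protocol, lists none. Protocol 10.4 says: "The SAP will serve as the final arbiter of all statistical analyses".

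**Downstream use.** SAP 7.7.1 also sets the duration rule: "Persistent organ failure is documented for greater or equal to 48 hours"; anything shorter is transient. SAP 7.9.1 and 7.10.1 take organ failure from Section 7.7 into the Revised Atlanta and determinant-based classifications, which are shown as frequency tables. Organ failure itself is only listed (SAP 7.7.3).

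**The concern.** A criterion for respiratory failure should depend on how well the patient oxygenates. Above a certain FiO2, this one depends only on how much oxygen is being given. Treatment is open-label, supportive care follows guidelines and local practice, and I found no saturation target or oxygen titration rule in either document. A well-saturated patient kept on 3 L/min would be classed as having organ failure, while the same patient on 2 L/min would not.

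One failing organ is enough for organ failure overall. If the episode lasts 48 hours or more, the patient is Revised Atlanta Severe and at least Severe on the determinant-based scale. If it is shorter, the grade is at least Moderately Severe or Moderate. A patient in this state at baseline also drops out of new persistent organ failure, which SAP 7.7.1 restricts to patients without organ failure at baseline. A difference in oxygen practice between arms or sites could then look like a difference in disease severity. Protocol 1.6 intends a dose-response look at efficacy, and Protocol 3.1 has available efficacy data reviewed before Cohorts 3 and 4 open.

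**Working it through.** **Inputs.** Cut-offs of 315 and 300 (Appendix 1); FiO2 by device and flow (Table 5); cohort sizes and 3:1 allocation (Protocol 3.1). The documents do not derive 315, so there is no planned figure to reproduce.

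**Step 1. When is the criterion automatic?** The highest possible ratio is 100/FiO2. The SpO2 at or below which the criterion is met is 315 × FiO2. The PaO2 at which PaO2/FiO2 equals 300 is 300 × FiO2.

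| Source | FiO2 | Highest ratio | SpO2 that meets the criterion | PaO2 (mmHg) at PaO2/FiO2 = 300 |
|---|---|---|---|---|
| Room air | 0.21 | 476.2 | ≤66.15% | 63 |
| Cannula 1 L/min | 0.24 | 416.7 | ≤75.6% | 72 |
| Cannula 2 L/min | 0.28 | 357.1 | ≤88.2% | 84 |
| Cannula 3 L/min | 0.32 | 312.5 | any (cut 100.8%) | 96 |
| Cannula 4 L/min | 0.36 | 277.8 | any | 108 |
| Cannula 6 L/min | 0.44 | 227.3 | any | 132 |
| Face mask 5 L/min | 0.40 | 250.0 | any | 120 |
| Face mask 8–10 L/min | 0.60 | 166.7 | any | 180 |
| Reservoir 10 L/min | 0.95 | 105.3 | any | 285 |

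The threshold is 100/315 = 0.3175, so every recorded FiO2 of 31.75% or more meets the criterion. Table 5 has 6 + 6 + 5 = 17 supplemental settings; 4 + 6 + 5 = 15 are automatic. One step from 2 to 3 L/min moves the requirement from SpO2 ≤88.2% to no requirement.

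**Step 2. Can an ABG correct it?** Not under Appendix 1, because the routes are alternatives. At 3 L/min, a patient with PaO2 above 96 mmHg passes the ABG route and still fails on SpO2/FiO2. Protocol 8.11.6 records ABGs only if already done, on Days 1, 5 and 10, so 10 − 3 = 7 of the ten assessment days have none recorded under that section.

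**Step 3. Does it carry into the SAP?** That depends on the missing conversion.
- *Assumption A: the conversion increases with the ratio and maps 315 to 300, the two cut-offs Appendix 1 lists together.* Then 312.5 maps to 300 or less: failure. Proportional scaling gives 312.5 × 300/315 = 297.6.
- *Assumption B: another function of the ratio alone.* A ratio of 312.5 arises from 100% on 0.32 and from 87.5% on 0.28 (87.5/0.28 = 312.5). No such function can separate these two patients.
- *Assumption C: a conversion using SpO2 and FiO2 separately.* If it returns PaO2 above 96 mmHg near 100% saturation on 0.32, the patient is not a failure. How it treats saturations near 100% then decides the result, and the SAP does not say.

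**Step 4. Size.** Planned groups: supportive care 1 + 1 + 2 + 2 = 6; lower dose 3 + 3 = 6; higher dose 6 + 6 = 12. One patient regraded moves a proportion by 1/6 = 16.7 points or 1/12 = 8.3 points.

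**Step 5. Baseline.** Inclusion 2a admits "a SpO 2 <97% with a FiO 2 ≥28" per cent. A patient at 96% on 32% qualifies and has a ratio of 96/0.32 = 300, so is already in respiratory failure under Appendix 1.

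**The case against.** The strongest objection is that the criticised rule is not the analysis rule: the SAP governs and does not contain 315. This stands in part. Whether the automatic failure reaches the analysis is undetermined. But the SAP supplies no alternative, and the only pairing in the documents carries the problem over.

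A reader might infer more than the documents support:
- *That oxygen flow determines the organ-failure and severity endpoints.* It is one sufficient trigger. Renal and cardiovascular failure, ventilation, necrosis, local or systemic complications and duration also decide the grades.
- *That every patient on 3 L/min or more is caught.* Flow converts to FiO2 only on uncontrolled sources. On controlled ones the trigger is the device's FiO2.
- *That 15 of 17 settings measures misclassification.* It counts table entries, not patients. At the higher FiO2 values PaO2/FiO2 is also 300 or less unless PaO2 is high (above 180 mmHg at 0.60), so many of these patients could fail by ABG as well.
- *That inclusion 2a contradicts Appendix 1.* One is an entry screen with SIRS as an alternative route, the other an outcome definition. They need not share a threshold.
- *That PASS gains 100 points.* SAP 7.3.1 specifies PaO2/FiO2 and does not say it is derived from SpO2.

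It is also fair that the primary endpoints are safety, that no tests are planned for these variables, and that the listings show the defining variables, so a reader can see which criterion was met. The two frequency tables do not show that. These points lower the severity; they do not remove the fault.

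**Conclusion.** Wrong as written; moderate severity. Under Appendix 1 with Table 5 it is certain that an FiO2 of 31.75% or more, which means 3 L/min or more on an uncontrolled source, gives respiratory organ failure at any saturation. It is conditional that this enters the analysis: it does if the SAP conversion keeps 315 equivalent to 300, and it may not otherwise. The effect on grade follows from the 48-hour rule, at 16.7 or 8.3 percentage points per patient regraded. The documents give no figure for how many patients would be well saturated at such an FiO2, or for how long, so the number affected cannot be estimated. No effect on PASS is established.

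**What to change.** In Appendix 1 and SAP 7.7.1:
1. Reconcile the two into one respiratory definition, and state the SpO2-to-PaO2 conversion, including its handling of saturations near 100%.
2. Let a recorded ABG PaO2/FiO2 take precedence over the SpO2-based value for the same assessment.
3. Flag every respiratory failure that rests only on the SpO2-based criterion with SpO2 of 97% or more, no ABG and no ventilation. The 97% is borrowed from inclusion 2a as a flagging limit, not as a new definition of failure.
4. Present the Revised Atlanta and determinant-based tables, and new persistent organ failure, with flagged assessments counted as failure and then as not failure.
5. Apply the same flag to the SOFA respiration item, whose PaO2/FiO2 is also estimated from SpO2/FiO2 (Protocol Appendix 2).

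This changes classification only, not patient care. The cost is wording, one sensitivity version of two tables, and the second count of new persistent organ failure. SpO2, FiO2 and ventilation are already recorded, as are the ABGs that exist. The downside is that many flagged assessments will stay unresolved, because ABGs are recorded only when done as standard care on Days 1, 5 and 10. The paired tables show how much that matters.
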